## Interventions

### Arch-Clamping Technique under Mild Hypothermia

This procedure is performed under mild hypothermia. The branch arteries of the arch are reconstructed using the side arms of a Y-shaped graft, which allows bilateral antegrade cerebral perfusion (bACP) through the right axillary artery. A FET is deployed in the descending aorta and clamped together with the autologous aorta immediately, then distal perfusion is restored through the femoral artery. After the proximal procedures is completed, the distal anastomosis is performed in an end-to-end fashion. Finally, the main trunk of the Y-shaped graft is anastomosed to the proximal grafts.

### Arch-Clamping Technique under Moderate Hypothermia

This procedure is performed under moderate hypothermia. The branch arteries of the arch are reconstructed using the side arms of a Y-shaped graft, which allow bACP through the right axillary artery. A FET is deployed in the descending aorta and clamped together with the autologous aorta immediately, then distal perfusion is restored through the femoral artery. After the proximal procedures is completed, the distal anastomosis is performed in an end-to-end fashion. Finally, the main trunk of

the Y-shaped graft is anastomosed to the proximal grafts.

### **Sun's Procedure using bACP**

Sun's procedure is performed using bACP under MHCA, which involves FET deployment in the descending aorta followed by total arch replacement with a four-branched vascular graft. Deployment of the FET and suture of distal anastomosis are completed during bACP. MHCA is terminated and distal reperfusion is initiated once the distal anastomosis is completed, and the left carotid artery is reconstructed first (after which bACP is stopped, rewarming is started and the brain is perfused bilaterally). The root or valve procedures and some concomitant operations, if indicated, are performed during the cooling phase.

### **Study Procedures**

#### **Study Flowchart**

Point Items	Point 1	Point 2	Point 3	Point 4	Point 5	Point 6	Point 7
	Enrollment	Treatment			Follow-up		
	Emergency Admission	Operati on Day	Post-op Day 1	Post-op Day 2-3	Discharg e/30 ±7 Days	6 months ±7 days	12 months ±7 days
Informed Consent	X						
Medical History & Demographics	X						
Symptoms & Physical Examination	X		X	X	X		
Laboratorial Biomarkers							
Hemogram	X		X	X	X	X	X
Coagulation	X		X	X	X	X	X
Myocardial Injury	X		X	X	X	X	X
BNP	X		X	X	X	X	X
Liver Function	X		X	X	X	X	X
Renal Function	X		X	X	X	X	X
Electrocardiogram	X				X	X	X
Imaging Index	X				X	X	X
Primary Outcome *							
MAEs			X	X	X	X	X
Secondary Outcomes					X		
Circulatory Arrest Time		X					
CPB Time		X					
Duration of MV			X	X	X		
Length of ICU Stay			X	X	X		

\* Primary Outcome which include death, renal replacement therapy, stroke, and paraplegia;  
 MAEs, Major adverse events; RRT: Renal replacement therapy; CPB, Cardiopulmonary Bypass; MV: Mechanical Ventilation.

## Study-Related Assessments

### Medical History and General Information

- (1) Demographics: Age, sex, height, weight, body mass index (BMI), body surface area (BSA).
- (2) Medical History: History of hypertension, coronary artery disease and treatment, diabetes mellitus and treatment, neurological complications and treatment, chronic obstructive pulmonary disease, chronic renal failure and treatment, thyroid dysfunction, peripheral vascular disease, history of cirrhosis or gastrointestinal bleeding, family history of hereditary aortic diseases (Marfan syndrome, Loeys-Dietz

syndrome, vascular Ehlers-Danlos syndrome, familial thoracic aortic aneurysm and dissection, etc).

## Symptoms and Physical Examination

(1) Symptoms: Location and quality of pain; concomitant symptoms such as dizziness, syncope, amaurosis, numbness or motor impairment of the limbs, abdominal distension, melena, or hematochezia.

(2) Physical Signs: Presence or absence of femoral and dorsalis pedis artery pulses; presence or absence of bowel sounds (noting hyperactive or absent sounds); color and skin temperature of the extremities.

## Preoperative Laboratorial Tests

(1) Complete blood count: Hemoglobin, white blood cell count, neutrophil count, neutrophil percentage, C-reactive protein, platelet count;

(2) Biomarkers of coagulation function: D-dimer, fibrinogen;

(3) Biomarkers of myocardial injury: Myoglobin, troponin, creatine kinase-MB, creatine kinase, lactate dehydrogenase, B-type natriuretic peptide;

(4) Biomarkers of liver function: Albumin, alanine aminotransferase, aspartate aminotransferase, total bilirubin, direct bilirubin.

(5) Biomarkers of renal function: Serum creatinine, creatinine clearance rate, uric acid, cystatin C;

(6) Arterial blood gas analysis: PaO2, PaCO2, arterial oxygen saturation, arterial potassium, arterial lactate.

## Preoperative Electrocardiogram and Imaging Indicators

(1) Electrocardiogram (ECG): Assess for signs of myocardial ischemia or infarction.

(2) Echocardiography

- Measure diameters of the aortic sinus, ascending aorta, arch, descending

artery, brachiocephalic artery, left common carotid artery (LCCA), and left subclavian artery (LSCA);

- Assess primary tear location and size, and involvement of the aortic sinus, ascending aorta, arch, descending aorta, brachiocephalic artery, LCCA, LSCA, and coronary arteries;
- Assess anatomic mutations of the aorta and its branches, such as aortic arch anomalies, coarctation, common origin of brachiocephalic and LCCA, aberrant subclavian artery, abnormal origin of vertebral artery, branch artery stenosis or tortuosity;
- Assess cardiac morphology and function: Ventricular sizes and motion abnormality;
- Assess aortic valve morphology and function: leaflet prolapse, regurgitation (degree, regurgitant neck, regurgitant area).

(3) CTA

- Measure the diameters of the aortic sinus, ascending aorta, arch, descending aorta, abdominal aorta (proximal and distal regions), and Vital abdominal arteries including celiac trunk artery, superior mesenteric artery, and renal arteries;
- Assess the involvement of dissection and entry tears in the aortic sinus, ascending aorta, arch, proximal and distal arch, descending thoracic aorta, abdominal aorta (proximal and distal), brachiocephalic artery, left common carotid artery, and left subclavian artery;
- Assess anatomic variations of the aorta and its branch vessels, such as aortic arch anomalies, coarctation, common origin of the brachiocephalic and left common carotid arteries, aberrant subclavian artery, abnormal origin of the vertebral artery, branch artery stenosis or tortuosity, and severe ischemia of the aorta or its branches.

**ECG and Imaging at Discharge / Postoperative Day 30, 6 Months, and 12**

## Months

- (1) ECG: Assess for myocardial ischemia or infarction.
- (2) Echocardiography
  - Measure diameters including the aortic sinus, ascending aorta, arch, descending aorta, brachiocephalic artery, LCCA, and LSCA;
  - Assess cardiac morphology and function: Ventricular sizes and motion abnormality;
  - Assess aortic valve morphology and function: Leaflet prolapse, regurgitation (degree, regurgitant neck, regurgitant area), presence of paravalvular or anastomotic leaks.
- (3) CTA
  - Measure the diameters of the aortic sinus, ascending aorta, arch, descending aorta, abdominal aorta (proximal and distal regions), and Vital abdominal arteries including celiac trunk artery, superior mesenteric artery, and renal arteries;
  - Assess for anastomotic leak, pseudoaneurysm formation, or prosthetic graft stenosis.

## Laboratorial Tests on Postoperative Day 1

- (1) Complete blood count: Hemoglobin, white blood cell count, neutrophil count, neutrophil percentage, C-reactive protein, platelet count;
- (2) Biomarkers of coagulation function: D-dimer, fibrinogen;
- (3) Biomarkers of myocardial injury: Myoglobin, troponin, creatine kinase-MB, creatine kinase, lactate dehydrogenase, B-type natriuretic peptide;
- (4) Biomarkers of liver function: Albumin, alanine aminotransferase, aspartate aminotransferase, total bilirubin, direct bilirubin.
- (5) Biomarkers of renal function: Serum creatinine, creatinine clearance rate, uric acid, cystatin C;
- (6) Arterial blood gas analysis: PaO2, PaCO2, arterial oxygen saturation, arterial

potassium, arterial lactate.

## **Laboratorial Tests on Postoperative Days 2-3 and Discharge / Postoperative 30**

### **Days ( $\pm 7$ days)**

- (1) Complete blood count: Hemoglobin, white blood cell count, neutrophil count, neutrophil percentage, C-reactive protein, platelet count;
- (2) Biomarkers of coagulation function: D-dimer, fibrinogen;
- (3) Myocardial injury markers: Myoglobin, troponin, B-type natriuretic peptide;
- (4) Biomarkers of liver function: Albumin, alanine aminotransferase, aspartate aminotransferase;
- (5) Biomarkers of renal function: Serum creatinine, creatinine clearance rate, uric acid, cystatin C.

### **Laboratorial Tests at Postoperative 6 Months ( $\pm 7$ days) and 12 Months ( $\pm 7$ days)**

- (1) Complete blood count: Hemoglobin, white blood cell count, neutrophil count, neutrophil percentage, C-reactive protein, platelet count;
- (2) Biomarkers of coagulation function: D-dimer, fibrinogen;
- (3) Myocardial injury markers: Myoglobin, troponin, B-type natriuretic peptide;
- (4) Biomarkers of liver function: Albumin, alanine aminotransferase, aspartate aminotransferase;
- (5) Biomarkers of renal function: Serum creatinine, creatinine clearance rate, uric acid, cystatin C.

## **Study Implementation**

### **Visit Schedule and Procedures**

This study comprises 7 visit points, with the specific content of each point as follows:

#### **Visit 1: Emergency Admission**

- (1) Obtain signed informed consent from the subject.

- (2) Collect medical history and general information.
- (3) Collect symptoms and physical examination findings.
- (4) Collect laboratory tests including complete blood count, liver and renal function, etc.
- (5) Collect ECG and imaging data.
- (6) Verify inclusion and exclusion criteria. Eligible subjects are enrolled and assigned a randomization number, and randomized to Experimental Group 1, Experimental Group 2, or Control Group.

## Visit 2: Operation Day

- (1) All Subjects undergo TAR+FET procedure.
- (2) For subjects in the experimental groups undergo aortic repair using mild or moderate hypothermic aortic-clamping technique with bACP; for control group subjects, undergo aortic repair using Sun's procedure with bACP.
- (3) Record surgical details, including cross-clamping time, CPB time, circulatory arrest time, and type and volume of intraoperative blood transfusion.
  - Concomitant procedures: coronary artery bypass grafting, valve surgery, other procedures (branch arterial bypass, aortic sinus procedures).
  - Cross-clamping clamping time: Time interval between ceasing and restarting cardiopulmonary bypass when core temperature reaches moderate hypothermia.
  - CPB time: Start-to-end time of cardiopulmonary bypass to complete aortic repair.
  - Circulatory arrest time: from cessation to resumption of circulation.
  - Type and volume of intraoperative transfusion of red blood cells, platelets, plasma, cryoprecipitate.

## Visit 3: Postoperative Day 1

- (1) Collect symptoms and physical examination findings.

(2) Collect laboratory tests, including complete blood count, biomarkers of liver and renal function, etc.

(3) Collect the occurrence of death, RRT, stroke, and paraplegia.

(4) Collect ICU parameters:

- Duration of mechanical ventilation: Time interval between mechanical ventilation and extubation after operation.
- Length ICU of stay: Time interval from ICU admission to transfer or death.

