### **Criteria and Process for Participant Withdrawal**

All participants who sign the informed consent and qualify for the trial, regardless of time and reason for withdrawal, will be considered early withdrawals if

they have not completed the observation period.

(1) Withdrawal by investigators decision.

- Serious adverse events occurred, and the investigators determine that the trial should be terminated.
- Participants suffering from complications and special physiological changes that render them unsuitable to continue the trial.
- Poor compliance.

(2) Voluntary Withdrawal.

- Participant is unwilling or unable to continue participation for any reason and requests withdrawal.
- Participant does not explicitly request withdrawal but refuses further treatment and/or follow-up.

(3) Handling of Early Withdrawal

- All early withdrawals must be documented in the case report form, including completion of the study summary page and reason for withdrawal. After early withdrawal, the investigator should make every effort to contact the subject, inquire about the reason for withdrawal, and complete as many assessment items as possible.

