#### **(1) Mortality**

**Definition:** Death occurring within 30 days postoperatively or before final hospital discharge, including transfer to other acute care facilities.

**Assessment Method:** For in-hospital events, clinical death is declared when the patient's electrocardiogram shows asystole and declared clinical death. For post-discharge events, death confirmed by telephone follow-up.

**Observation Time Points:** Discharge day / postoperative 30 days and 12 months.

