**Table 4. American Spinal Injury Association (ASIA) Impairment Scale**

Grade	Clinical Manifestations
A (Complete injury)	No sensory or motor function preserved.
B (Incomplete injury)	Sensory function is preserved below the neurological level, including the sacral segments, but no motor function is preserved.
C (Incomplete injury)	Motor function is preserved below the neurological level, but more than half of key muscles have a muscle grade less than 3.
D (Incomplete injury)	Motor function is preserved below the neurological level, and at least half of key muscles have a muscle grade of 3 or greater.
E (Normal)	Sensory and motor functions are normal.

Note: Muscle strength grading: 0-No movement in the lower limbs; 1-Lower limb movement cannot overcome gravity; 2-Limb movement can overcome gravity; 3-Able to stand with assistance; 4-Able to walk with assistance; 5-Normal.

**Observation Time Points:** Postoperative 1 to 3 days, and discharge day / postoperative 30 days.

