## **Criteria for Subject Exclusion**

### **FAS Exclusion Criteria**

- (1) Subjects who did not receive TAR+FET treatment after enrollment;
- (2) Subjects with no follow-up records.

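### The FAS exclusions, with no primary-event form on operation day, can remove a patient who dies in theatre or before the first postoperative visit instead of counting that death as an event

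*Combined protocol and SAP*

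**What the plan says.** **Schedule.** Under Visit Schedule and Procedures, Visit 2 (Operation Day) asks the site to "Record surgical details, including cross-clamping time, CPB time, circulatory arrest time, and type and volume of intraoperative blood transfusion". It does not ask for any primary event. The instruction "Collect the occurrence of death, RRT, stroke, and paraplegia" first appears at Visit 3 (postoperative day 1) and is repeated at Visits 4 to 7. The Study Flowchart agrees: the row for major adverse events, footnoted "Primary Outcome which include death, renal replacement therapy, stroke, and paraplegia", is marked from postoperative day 1 onward and is blank on operation day.

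**Endpoint.** The observation points for RRT, stroke and paraplegia are all "Postoperative 1 to 3 days, and discharge day / postoperative 30 days". Mortality is different. It is defined as "Death occurring within 30 days postoperatively or before final hospital discharge, including transfer to other acute care facilities" and is observed at "Discharge day / postoperative 30 days and 12 months".

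**Analysis set.** Analysis Populations describes the FAS as built on the intention-to-treat principle, but limits it to patients who received TAR+FET. FAS Exclusion Criteria removes (1) patients who did not receive TAR+FET after enrolment and (2) "Subjects with no follow-up records". Handling of Missing and Abnormal Values rules out imputation.

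**Withdrawal.** Patients who have not completed the observation period, "regardless of time and reason for withdrawal, will be considered early withdrawals if" that is so, are early withdrawals. No exception is made for death.

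**The concern.** The trial compares operative techniques, so a death during or just after the operation is the primary event closest to the intervention. Three parts of the protocol (the visit list, the flowchart and three of the four component observation points) begin on the following day, and the FAS rules do not say what happens to a patient who never reaches it. If such a death is removed, it leaves both the numerator and the denominator, and the arm in which it happened looks better. That would affect the superiority test of Group 1 against control and, through the fixed sequence, the non-inferiority test of Group 1 against Group 2. The trial is open-label, so any case-by-case decision on whether such a patient belongs in the FAS would be made with the arm known.

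**Working it through.** **1. Follow two patients through the rules.**

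| | Dies in theatre before the repair is complete | Dies after the repair, before Visit 3 |
|---|---|---|
| Meets the mortality definition? | Yes, a death before discharge | Yes |
| Primary-event form on operation day? | No | No |
| Received TAR+FET? | Arguable; FAS exclusion (1) can apply | Yes |
| Has follow-up records? | Undefined; FAS exclusion (2) can apply | Undefined; FAS exclusion (2) can apply |
| Any statement that the death stays in the FAS as an event? | None | None |
| Outcome imputed if blank? | No | No |

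The plan does not define follow-up records. The flowchart puts only discharge/30 days, 6 months and 12 months under the Follow-up heading; operation day and postoperative days 1 to 3 fall under Treatment.

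**2. The plan's own sample size.** Inputs from Estimation of Total Sample Size: 13% against 30%, one-sided 0.025, power 80%, 10% dropout. With a pooled z-test and mean rate 0.215:

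n = [1.960·√(2·0.215·0.785) + 0.842·√(0.13·0.87 + 0.30·0.70)]² / 0.17² = 90.5, so 91 per group.

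91/0.90 = 101.1, so 102 per group and 306 in total. Both figures reproduce, and this point changes neither.

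**3. Weight of one death.** 1/102 = 0.98 and 1/91 = 1.10 percentage points. The 5-point margin is 0.05 × 102 = 5.1 patients.

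**4. Can one lost death change a result?** The event counts are chosen for illustration. Upper 95% limit = d + 1.96·√[p₁(1−p₁)/n₁ + p₂(1−p₂)/n₂], where d = p₁ − p₂ and Group 1 comes first.

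| Test | All deaths counted | One Group 1 death lost | One lost in each arm |
|---|---|---|---|
| Superiority over control (limit must be below 0) | 17/102 v 28/102: +0.0050, fails | 16/101 v 28/102: −0.0040, passes | 16/101 v 27/101: +0.003, fails |
| Non-inferiority to Group 2 (limit must be below 0.05) | 20/102 v 26/102: 0.0556, fails | 19/101 v 26/102: 0.0471, passes | 19/101 v 25/101: 0.054, fails |
| Superiority, near the planned rates | 13/102 v 31/102: −0.066, passes | 12/101 v 31/102: −0.076, passes | – |

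**5. Expected shift under assumed death rates.** The documents give no operation-day death rate, so 0–5% per arm is an assumption. If a share r of an arm dies on operation day and is dropped, its event rate becomes (p − r)/(1 − r). The true difference is 0.13 − 0.30 = −0.170.

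| Assumed r, Group 1 / control | Rates after dropping | Difference |
|---|---|---|
| 1% / 1% | 12.1% / 29.3% | −0.172 |
| 5% / 5% | 8.4% / 26.3% | −0.179 |
| 3% / 1% | 10.3% / 29.3% | −0.190 |
| 1% / 3% | 12.1% / 27.8% | −0.157 |
| 5% / 0% | 8.4% / 30.0% | −0.216 |
| 0% / 5% | 13.0% / 26.3% | −0.133 |

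Equal loss moves the difference by less than one point. Unequal loss moves it towards the arm that loses more deaths, in either direction.

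**The case against.** A reader might infer that an operation-day death has no primary-outcome record at all, or that the schedule contradicts the endpoint. The documents support neither reading. Visits 3, 4 and 5 each ask whether death has occurred, which does not require a living attendee. Mortality is observed at discharge or 30 days, and a patient who died on operation day has a known status at that point. Death is also a serious adverse event reportable within 24 hours. A schedule that first records events the next day omits a form; it does not say that the death is not counted.

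Nor does the early-withdrawal label remove anyone from the FAS, because withdrawal is not among the FAS exclusions. Its effect would be on the per-protocol set, which is limited to patients who completed the trial.

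Two further objections also stand. If follow-up records means only the visits under the Follow-up heading, a day-2 death recorded at Visit 4 is equally exposed, so the weakness lies in the exclusion wording more than in Visit 2. Adding a tick on operation day alone would not cure it. The reversals in step 4 need a borderline result and loss from Group 1 only, and nothing in the documents suggests that loss would differ by arm.

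What remains is that none of these routes overrides the FAS rules. Safety reports go to the institution's management department and the ethics committee, and the plan does not link them to the primary-endpoint data. A death that is recorded can still be excluded.

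**Conclusion.** The point holds as a gap in the analysis-set rules, made worse by the missing operation-day form. As written, the FAS exclusions can remove a patient whose death meets the mortality definition, contrary to the intention-to-treat principle that the same section claims. Loss is possible, not certain. Each lost death is worth about 1 percentage point of an arm. Under assumed operation-day death rates of 0–5% per arm, dropping these deaths moves the planned difference of −0.170 to somewhere between −0.133 and −0.216. A test result would change only near its boundary; at about the planned rates, losing one Group 1 death leaves the conclusion as it was. The direction of any bias cannot be known in advance. The correction should be made because it is cheap and removes a decision that would otherwise be taken with the arm known.

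**What to change.** 1. **Analysis Populations and FAS Exclusion Criteria (the change that matters).** State that any randomised patient who dies from the start of the operation onward stays in the FAS as a primary event. State that death is a complete outcome, and is never grounds for treating the patient as lacking follow-up records, as not having received TAR+FET, or as an early withdrawal.
2. **Visit 2 and the Study Flowchart (support).** Add collection of death, RRT, stroke and paraplegia to Visit 2 and mark the major-adverse-event row in the Operation Day column, so that events from the operation onward are recorded. Leave the component definitions unchanged; paraplegia, for example, remains defined as a new postoperative injury.

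The cost is one extra eCRF item at an existing visit plus protocol wording. No procedure is added and the sample size stays at 102 per group. Observed event rates may be slightly higher.

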#### **Visit 4: Postoperative Days 2-3**

(1) Collect symptoms and physical examination findings.

(2) Collect laboratory tests, including complete blood count, biomarkers of liver and renal function, etc.

(3) Collect the occurrence of death, RRT, stroke, and paraplegia.

(4) Collect ICU parameters:

- Duration of mechanical ventilation: Time interval between mechanical ventilation and extubation after operation.
- Length ICU of stay: Time interval from ICU admission to transfer or death.

